Hypothesis (Reach): Individuals who are due for follow-up can be reached by mFOCUS irrespective of patient sociodemographic characteristics and "severity" of the screening result. Patient surveys will be used to examine barriers and facilitators.

Hypothesis (Adoption, Implementation, and Maintenance): mFOCUS will be *adopted* across providers/ practices and consistently *implemented*. Provider and system-level surveys will be used to examine barriers and facilitators to adoption, implementation and maintenance.

NOTE: This protocol involves patients who receive care at Partners (MGH and BWH) as well as Dartmouth. Dartmouth is the relying site on the Partners IRB review a SmartIRB reliance agreement has been put in place

BACKGROUND AND SIGNIFICANCE

Provide a brief paragraph summarizing prior experience important for understanding the proposed study and procedures.

In the United States (US), most cancer screening is initiated in primary care settings but requires care transitions with other providers who either perform the test or evaluate the result. Screening benefits are only realized through timely follow-up of abnormal breast, cervical, colorectal and lung screening results. Incomplete follow-up represents an ongoing challenge as the initial screening event transitions to diagnostic evaluations involving complex interactions among patients, primary care providers (PCPs), and specialists.

Our recent study within the NCI-funded Population-Based Research Optimizing Screening through Personalized Regimens (PROSPR) consortium reported significant rates of screening abnormalities that required additional evaluation, including; 11% of breast cancer, 8% of cervical and 5% of fecal occult blood test (FOBT)/ fecal immunochemical test (FIT) screens, consistent with other studies. The abnormality rates for colonoscopy screening (~20% adenomas) and lung cancer screening with low dose computed tomography (LDCT)'s are also high (~25%). Our work also demonstrates wide variation in follow-up rates across primary care clinics, that differ by cancer type as well as the "severity" of the screening abnormality (5 – 95% with an average of ~ 50% overall). Apart from the

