All individuals in this study will receive the current standard of care at Partners for the follow-up of abnormal cancer screening tests (Arms 1-4). In addition to this standard of care, we will test 3 additional arms of increasing intensity of intervention: Arm 2-access to an IT platform to facilitate updates to HM modifiers and problem lists for visit-based reminders; Arm 3- the IT platform in addition to automated reminders to patients (Patient Gateway messages or letters, one brief phone call or voice message) and the care team (bulk In-Basket messages); Arm 4-the IT platform, automated reminders, and administrative outreach and navigation to help with scheduling and to address social barriers to care.

Patients will only be recommended to receive care that is recommended by national guidelines/ local expert opinion. Our study is focused on ensuring that people get timely appropriate care. Since launching the study, we have found that there is a small number of patients who get care that is not supported by national guidelines. An example of this would be a woman with a high-grade cervical abnormality who gets a repeat pap smear and not a colposcopy. In some of these instances it is documented that the patient and their personal care team had a discussion of the harms and benefits of making an alternative choice, but in others there is no documentation of why alternative care was received.

If we find that a patient has received an alternative evaluation to the diagnostic evaluation recommended by national care guidelines and there is no documentation of informed decision making, the PIs will contact the patient's PCP and/or clinical director of the primary care practice and/or the institutional ambulatory team. This will be done for patients in any of the study arms. While these patients remain eligible for our study as they will not have achieved our primary outcome, we will not contact these patients in arms 3 and 4 to minimize confusion or anxiety for the patient. Because of the small number of patients we believe that ethically this is the right choice even though it may marginally decrease our power to find an effect across the study arms.

Describe how risks to subjects are minimized, for example, by using procedures which are consistent with sound research design and which do not unnecessarily expose subjects to risk or by using procedures already being performed on the subject for diagnostic or treatment purposes.

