We will protect against risks of psychological discomfort by using neutral language in patient surveys. To prevent loss of data, all information is stored within the Partners Healthcare System, Inc. firewall, password protected, and anti-virus software enabled (or Dartmouth for Dartmouth patients). Only study staff will have access to the study data on Shared File Areas. We do not anticipate any adverse effects from this study, but we will promptly report any problem to the IRB and address any problems accordingly.

Our study is focused on ensuring that people get timely appropriate care. Since launching the study, we have found that there is a small number of patients who get care that is not supported by national guidelines. An example of this would be a woman with a high-grade cervical abnormality who gets a repeat pap smear and not a colposcopy. In some of these instances it is documented that the patient and their personal care team had a discussion of the harms and benefits of making an alternative choice, but in others there is no documentation of why alternative care was received.

If we find that a patient has received an alternative evaluation to the diagnostic evaluation recommended by national care guidelines and there is

no documentation of informed decision making, the PIs will contact the patient's PCP and/or clinical director of the primary care practice and/or the institutional ambulatory team. This will be done for patients in any of the study arms. While these patients remain eligible for our study as they will not have achieved our primary outcome, we will not contact these patients in arms 3 and 4 to minimize confusion or anxiety for the patient. Because of the small number of patients we believe that ethically this is the right choice even though it may marginally decrease our power to find an effect across the study arms.

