After our study, we found that the Health Maintenance Modifiers we created were placed on 259 patients' charts by their clinicians (outside of our research). There is no functionality built in Epic to remove these modifiers when an appropriate follow-up test was received by a patient unless they were part of our study. Our study has now ended, and we have removed the health maintenance modifiers that we created. Because we didn't create the modifiers for these 259 patients, we are concerned that they will linger even if a patient has received appropriate follow-up. We will contact anyone in the Epic HMM Audit User list and ask them to review the modifier and either replace it with other functionality available in Epic or remove it. We will send 2-3 reminders over the course of 4-6 weeks. The last reminder will inform them that the modifier will be removed by our study staff.

Describe explicitly the methods for ensuring the safety of subjects. Provide objective criteria for removing a subject from the study, for example, objective criteria for worsening disease/lack of improvement and/or unacceptable adverse events. The inclusion of objective drop criteria is especially important in studies designed with placebo control groups.

This protocol is minimal risk, as it is designed to improve the quality of care for patients with an abnormal cancer screening test result that is overdue for follow-up. Automated outreach (by Patient Gateway or letters) will provide information for patients to contact their PCP's office to arrange for needed follow-up. Patients in Arm 4 who are contacted by the study outreach administrator or navigator who say that they do not want further evaluation will not be contacted further by study staff. Participants selected for the surveys will be informed that they can refuse participation at any point.

FORESEEABLE RISKS AND DISCOMFORTS

Provide a brief description of any foreseeable risks and discomforts to subjects. Include those related to drugs/devices/procedures being studied and/or administered/Performed solely for research purposes. In addition, include psychosocial risks, and risks related to privacy and confidentiality. When applicable, describe risks to a developing fetus or nursing infant.

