PCP surveys will be sent by email via a RedCap Survey link, that will include a gift card code. The pre-trial surveys will be sent electronically during the 3 months before the trial. Post-trial surveys will be sent electronically during the 3 months following the trial. Because the trial will run for 2 years it may be different doctors who are asked to complete the survey. The consent process for the 2 surveys will be done independently because the long period of time in between.

Patient surveys: As noted above, we will randomly sample 15% of participants. Patient surveys will be administered 4-12 weeks after their individual follow-up period has been completed, so surveys will be conducted throughout the enrollment period. *Survey procedures* will include: 1) an introductory letter from the clinical director of each primary care network paired with a letter from the PI that explains the study purpose and opportunities to opt out/ participate of the survey (see attached). Patients will be given the opportunity to go to a unique Redcap url/QR code from the letter or will receive an un-secured email. The letter will include contact directions to email/ phone study staff if they do not wish to opt-out of the survey or do not wish to receive un-secured email. Those who do not opt-out within 2 weeks will be contacted by phone and asked to complete the survey by phone or RedCap. If the patients opt for the later, they will receive the survey link via un-encrypted email (and asked for the email where they would like to receive it). Patients will receive up to 5 email/mail attempts over 4 weeks followed by up to one phone call. All mail surveys will be sent with a pre-addressed envelope with pre-paid postage.

Remuneration is described in the appropriate section below.

Provide details of remuneration, when applicable. Even when subjects may derive medical benefit from participation, it is often the case that extra hospital visits, meals at the hospital, parking fees or other inconveniences will result in additional out-of-pocket expenses related to study participation. Investigators may wish to consider providing reimbursement for such expenses when funding is available

Subjects in the main trial will not receive remuneration.

Patients who are sampled for the survey and complete the survey will receive a \$50 gift card from their choice of Amazon or a regional grocery store.

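### Study staff are to clear leftover Health Maintenance Modifiers as the default step, with no stated check that follow-up has taken place

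*Combined protocol and SAP*

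**What the plan says.** The text is in the protocol under Research Design and Methods, in the answer on how risks to subjects are minimized. After the trial, the team found that clinicians had placed the study-built modifiers on 259 charts outside the research. The modifiers the study itself had placed have already been taken off.

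For the 259 the protocol explains: "There is no functionality built in Epic to remove these modifiers when an appropriate follow-up test was received by a patient", with an exception only for study patients. It then names its worry: "we are concerned that they will linger even if a patient has received appropriate follow-up".

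The plan that follows has three steps:
- Contact everyone on the Epic audit user list for these modifiers, and ask them to review each one and either put other Epic functionality in its place or take it off.
- Send 2-3 reminders over 4-6 weeks.
- Close with the default: "The last reminder will inform them that the modifier will be removed by our study staff".

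The answer on standard of care, in the same part of the protocol, shows what the modifiers are for. Arm 2 is described as an IT platform that facilitates "updates to HM modifiers and problem lists for visit-based reminders".

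**The concern.** The reason and the action do not cover the same patients. The reason concerns patients whose follow-up is complete, for whom a modifier left on the chart is out of date. The default action applies to every modifier still in place after the last reminder, and nothing limits it to patients with follow-up on record.

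For a patient still overdue, the modifier is doing its job. Removing it takes away a prompt that the patient's own clinician chose to place, for an abnormal cancer screen not yet worked up. That is the care gap the trial was set up to close, and here the removal would be an act of study staff. The protocol discusses the risk of leaving a modifier on too long. It does not discuss the risk of taking one off too soon.

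**Working it through.** No sample size, power or error-rate figure bears on this point, and 259 is a stated count with no inputs from which to reproduce it. The check is a reading of the text, plus one bound and one cost ratio.

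**1. Does a remaining modifier show follow-up status?** No. For these 259 patients Epic does not clear the modifier when a follow-up test is received. A modifier still present is therefore compatible with completed follow-up and with overdue follow-up. The two can be told apart only by looking at the record.

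**2. Reason and action side by side.**

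| Patient's status when reminders end, no clinician action | Covered by the stated reason? | Covered by the default removal? |
|---|---|---|
| Appropriate follow-up received | Yes | Yes |
| Still overdue | No | Yes |

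The second row is the gap.

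**3. Is a check stated anywhere else?** I found none in the protocol or the SAP. No text has study staff establish follow-up status before removal or treat overdue patients differently at that step. No escalation beyond the listed users is stated for when nobody acts.

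**4. Size.** The number of patients who could lose the prompt while overdue is

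N = 259 × (share with no clinician action) × (share of those still overdue).

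The documents give neither share. Each lies between 0 and 1, so N lies between 0 and 259 × 1 × 1 = 259. The upper end requires that no clinician acts on any chart and that every patient is overdue.

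**5. Cost of a look-up.** At most 259 charts. The protocol's enrollment text allows for up to 20,000 chart reviews study-wide, and 259 / 20,000 = 1.3%. The inclusion criteria already define need for follow-up by the absence of an appropriate test in the EHR within a specified time, so the study has a working definition to apply.

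**The case against.** The strongest reply is that clinicians decide first. They are asked to review each modifier, may replace it with another Epic tool, are reminded 2-3 times and are told in advance that it will be removed. Patients stay under their own clinicians, so what may go is one prompt and not their follow-up care. All of this stands, and it confines the concern to charts on which no listed user acts. It does not answer the concern for those charts.

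The absence of a check is also inferred from silence. The protocol reports what the last reminder will say. It does not describe how staff carry out the removal, nor does it spell out that removal depends on non-response, although that is the natural reading. The supportable statement is that no check is stated, not that none will be made.

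Three stronger readings are tempting, and the documents do not support them:

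- **A contradiction with the escalation route.** When a patient is found to have had an alternative evaluation without documented informed decision making, the investigators contact the PCP "and/or clinical director of the primary care practice and/or the institutional ambulatory team". That route covers patients in the study arms. The 259 were flagged outside the research. At most, safeguards differ between two populations.
- **Non-response through staff turnover.** The recruitment section says "Because the trial will run for 2 years it may be different doctors who are asked to complete the survey". That sentence concerns who answers the PCP surveys. It gives no departure or non-reply rate for users on the audit list.
- **A patient count from the background rate.** The Background section reports follow-up across clinics "with an average of ~ 50% overall", and a reader might multiply 259 by the complement. That average spans clinics, cancer types and severities. It does not describe patients whose clinicians had already flagged them, and the product would also assume that nobody replies.

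Finally, judging whether follow-up was appropriate depends on the organ and the abnormality, and the 20,000 reviews serve a different task. The look-up is therefore small but not free.

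**Conclusion.** The point holds as a minor patient-safety gap in post-trial clean-up. Followed as written, the default step can remove a clinician-placed prompt from a patient who is still overdue, although the only reason given for removal applies to patients who are not.

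The number affected is at most 259 and cannot be estimated from the documents. The conclusion rests on two readings: that staff removal follows when no listed user has acted, and that the lack of a stated check means the plan does not require one. If staff already look up follow-up status in practice, only the text needs correcting.

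A reader might infer that the trial's results are affected. Nothing here supports that: these modifiers were placed outside the research, the step comes after the study ended, and no effect on the primary analysis, significance level or power follows from it.

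**What to change.** Reconcile the removal step with its stated reason. Before removing a modifier that no clinician has acted on, have existing study staff look up whether appropriate follow-up is documented, using the study's own definitions. The protocol should then distinguish patients with documented follow-up from those without, and state what happens for each group. How patients without documented follow-up are handled is for the investigators, practices and IRB to decide.

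The cost is a short change to the protocol text and a record look-up on at most 259 charts, fewer if clinicians respond. Some modifiers will stay in place slightly longer, including some that are already out of date. The contact plan is written in the future tense, so on the text as it stands the change can still be made.

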# of days to completion of required diagnostic evaluation (EHR/ claims)	
Satisfaction with follow-up care (patient survey)	
Knowledge of test result and need for follow-up (patient survey)	PCP-Reported Assessment of:
Satisfaction with ability of patients to get timely follow-up (PCP survey)	Individual-Patient: Patient understanding of need for follow-up
Time required for management (PCP survey)	Care Team: Satisfaction with coordination of care
	System: Satisfaction with IT functionality to support follow-up

Analysis Plan/ Sample Size. Our primary analysis will be intention-to-treat (ITT). All eligible, enrolled patients will be part of the ITT cohort. We expect that a small number of patients may change primary care clinics within our systems. These individuals will be evaluated according to their initial intervention status. Prior to analysis, all data will be examined for accuracy, logical consistency and missing data. We expect complete data for intervention status and our outcomes. We will use multiple imputation, using the MI procedure in SAS, to account for any missing values of covariates. Through the stratified randomization we will attempt to balance patient, provider and practice characteristics between study groups. However, since randomization occurs at the practice level, we will be cautious and still compare the patient, provider and practice characteristics using Fisher exact tests, t-tests and Wilcoxon tests as appropriate to the covariate distribution. Any characteristics that show substantial clinical or statistical difference ($p < .05$) will be entered into the regression model and retained as covariates if they alter the effect estimate of the intervention by $> 20\%$.

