The primary analysis model will be a random effects logistic regression, implemented through the SAS Glimmix procedure. Timely follow-up (yes/no) will be the patient-level outcome and random effects for practice and physician will allow for exchangeable correlation between patients seen within the same practice and by the same physician. The primary fixed predictors will be 3 indicator variables representing the 3 intervention arms and we will use a global likelihood ratio test to compare the 4 study arms. If the global test is significant ($p < 0.05$), we will compare the intervention arms to the control group (our primary comparisons with a Bonferroni-adjusted significance level of 0.0167) and to each other (secondary comparisons). Comparisons to the control arm will capture the cumulative effects of the interventions, while comparisons between the intervention arms will capture the marginal effects of each level of intervention. We will include covariates for the type of cancer, level of initial screening abnormality, and any patient, provider or practice characteristics which are identified as confounders.

Results will be presented as adjusted follow-up rates, with 95% confidence intervals, calculated using marginal standardization.

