In discussions (but not in the protocol), there was interest in exploring how COVID affected the outcome, in the sense that patients who became eligible when COVID was more prevalent (and elective care was less available) may have taken longer to have follow-up. Because this is a complicated topic and will distract from the main randomized results, it was decided to save such analyses for a subsequent manuscript. The current manuscript will simply adjust (through indicator variables) for 3-month time windows. Since COVID peaked in different areas at different times, these indicator variables will be included as interactions with study site (Boston versus Dartmouth).

Contents:

1. Exhibit 1: Figure 1: Consort Diagram
2. Exhibit 2: Table 1: Baseline Characteristics, by Arm
 - a. Patient characteristics
 - i. Sex
 - ii. Age
 - iii. Race/Ethnicity
 - iv. Primary insurance
 - v. Primary language
 - vi. Marital status
 - vii. Comorbidities
 - viii. Number of PCP visits in prior year
 - ix. Number of no show visits in prior year
 - x. Type of cancer
 - xi. Severity of screening abnormality
 - xii. Rurality (distance or population)
 - xiii.
 - b. PCP characteristics (from protocol; none currently in the prototype table):
 - i. Sex
 - ii. Provider type (MD/ DO, NP/ PA, other)
 - iii. Specialty
 - iv. Panel size (not risk adjusted)

- c. Clinic characteristics (from protocol; none currently in the prototype table):
 - i. Location (hospital; community health center)
 - ii. Visit volume at time of randomization
 - iii. Patient mix (% female; % Medicaid) at time of randomization

- 3. Exhibit 3: Table 2: Overall Primary (120 day completion) and secondary (240 day) outcome analyses
Intent-to-Treat and Modified Intent-to-Treat;
“Unadjusted” and Adjusted
 - a. Presentation: Data will be shown by arm, both ITT and mITT, both adjusted and “unadjusted”
 - i. The overall global p-value (<0.05) for the adjusted ITT analysis will be shown. If the global test is significant, then three pairwise tests (each arm against control/Arm 1) looking for $p<0.0167$.
 - ii. All other analyses and comparisons will be based on 95% confidence intervals

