 - b. Primary and secondary analyses: SAS Proc GLIMMIX with the patient as the unit of analysis and a binary outcome (completed/not completed). All models (including “unadjusted”) will include random effects for practices and physicians. All models (including “unadjusted”) will include fixed effects for type of cancer. All models (including “unadjusted”) will include indicator variables for time (calendar month), along with interaction terms with site (Boston versus Dartmouth).
 - i. Unadjusted analysis: The model above will include random effects for practices and physicians, fixed effects for cancer types, fixed effects and interactions for calendar month and study stie, and indicator variables for Arms 2, 3, and 4.

 - ii. Adjusted analysis: The covariates from 2 above will be added individually to the model. Any that are significant at $p<0.05$ and change the coefficient of any of the 3 indicators for treatment arm by $>20\%$ will be retained in the model as confounders. (Type of cancer and calendar month will be retained in the model regardless of significance or confounding.) Adjusted completion rates will be calculated by marginal standardization and presented in the Table.

- 4. Exhibit 4: Figure 2: Forest plot with subgroup analyses for the primary (120 day completion) outcome

Intent-to-Treat
Adjusted only

- a. Presentation: Data will be shown by subgroup as an odds ratio (versus the control arm 1) with 95% confidence interval; ITT; adjusted only
 - i. P-values for interaction will be presented
 - ii. All other comparisons will be based on 95% confidence intervals
- b. Subgroup analyses: SAS Proc GLIMMIX with the patient as the unit of analysis and a binary outcome (completed/not completed). All models will include random effects for practices and physicians. All models will include fixed effects for type of cancer and calendar month.
 - i. Subgroups (each set analyzed separately):
Type of cancer (breast; cervical; CRC; lung)
Severity of abnormality (low; medium; high)
 - ii. Adjusted analysis: The model above will include random effects for practices and physicians, fixed effects for cancer types and calendar month, indicator variables for Arms 2, 3, and 4, indicator variables for the subgroups, and interaction terms for the arms-by-subgroups.
A global test for effect modification will be run and reported. However, regardless of significance, a separate “unadjusted” model will be run for each subgroup.

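### The covariates of the adjusted model that carries the primary test are defined differently in the protocol and the SAP, and the SAP gives two units for its forced time term

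*Combined protocol and SAP*

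**What the plan says.** **Where the test sits.** SAP Contents item 3.a.i: "The overall global p-value (<0.05) for the adjusted ITT analysis will be shown". If that test is significant, each intervention arm is compared with control at p<0.0167.

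**Protocol, Analysis Plan/ Sample Size.** Characteristics are first compared between study groups. "Any characteristics that show substantial clinical or statistical difference" (p below .05 for the statistical route) "will be entered into the regression model and retained as covariates if they alter the effect estimate of the intervention by" more than 20%. The description of the primary model adds two fixed terms: "We will include covariates for the type of cancer, level of initial screening abnormality", together with any characteristic identified as a confounder. It has no calendar-time term.

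**SAP Contents item 3.b.ii.** "The covariates from 2 above will be added individually to the model", where item 2 is the list of baseline characteristics in Exhibit 2. A covariate stays only if it is significant at p<0.05 and would "change the coefficient of any of the 3 indicators for treatment arm by" more than 20%. Two terms are protected: "Type of cancer and calendar month will be retained in the model regardless of significance or confounding". Severity of the abnormality is item 2.a.xi of the candidate list.

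**Calendar time within the SAP.** The Comments paragraph on COVID says: "The current manuscript will simply adjust (through indicator variables) for 3-month time windows", interacted with study site. Item 3.b specifies calendar month, also interacted with site, in every model.

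**The concern.** The trial's primary conclusion should come from one model that can be written down before the arm comparison is seen. Here, someone following the protocol and someone following the SAP can fit different models to the same data, and the SAP alone leaves the time term open. With three pairwise tests at 0.0167, a change of covariate set can move a borderline comparison across the line. The choice also reaches secondary results. The protocol tells the time-to-follow-up model to identify covariates in the same way as its primary model, SAP item 5.c tells the Cox model to use the SAP's logistic set, and SAP item 3.b covers the 240-day outcome as well.

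**Working it through.** **1. The two rules side by side**

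| Feature | Protocol, Analysis Plan | SAP 3.b.ii |
|---|---|---|
| Which covariates are tried | Those imbalanced between arms | All in Exhibit 2, one at a time |
| Meaning of the 0.05 criterion | Difference between arms at baseline | Significance on being added to the outcome model |
| Clinical route to entry | Yes, no threshold given | None |
| Change criterion | >20% in the intervention effect; which of three arms is not said | >20% in any one of three arm coefficients |
| Cancer type | Always in | Always in |
| Severity | Always in | Candidate, can be dropped |
| Calendar time by site | Not mentioned | Always in; unit stated two ways |

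The rules share cancer type and the 20% criterion. They conflict on the 0.05 criterion, the clinical route and severity. An imbalanced covariate unrelated to outcome can pass the protocol's first step and fail the SAP's. A strongly prognostic, roughly balanced covariate can do the reverse.

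**2. Size of the time-term discrepancy.** The protocol (Recruitment Procedures) says the trial will run for 2 years. With two sites (Boston, Dartmouth), parameters = (periods − 1) + 1 site + (periods − 1) interactions.
- Month: 23 + 1 + 23 = 47.
- 3-month window: 7 + 1 + 7 = 15.

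**3. What a 20% change means.** Assume 50% completion under control, the overall average in the protocol's background section. The gate is 0.20 × logit(0.50 + d), since logit(0.50) = 0.
- d = 11 points: 0.20 × ln(0.61/0.39) = 0.20 × 0.447 = 0.089.
- d = 14 points: 0.20 × ln(0.64/0.36) = 0.20 × 0.575 = 0.115.
- d = 2 points: 0.20 × ln(0.52/0.48) = 0.20 × 0.080 = 0.016.

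The gate at 11 points is 0.089/0.016, or about 5.6 times, as high as at 2 points. Whether a covariate stays therefore depends on the estimated treatment effect. This applies to both rules, so it is an argument for a fixed list and not part of the conflict.

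**4. Illustration by simulation (assumed inputs).** From the documents: 44 practices (the stated maximum), about 75 patients each (3324/44 = 75.5), 24 months, 25% of practices at Dartmouth (from 9,000 of 12,000 at the Boston networks), and stratification on the three randomisation factors. Assumed: practice ICC 0.02 or 0.05, physician ICC 0.02, completion of 30/50/70% by severity, and 18 other covariates at 0 to 0.2 log-odds per SD. There were 230 replicates per scenario (standard error about 1 to 3 points). Both rules used the same 3-month-by-site term. Cells give the percentage of trials in which the two rules disagree, at ICC 0.02/0.05.

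| Arm effects (points) | Protocol entry read as | Any of four verdicts | Global verdict |
|---|---|---|---|
| +11/+12.5/+14 | p<.05 or standardised difference >0.2 | 10.0/20.4 | 1.7/7.4 |
| +11/+12.5/+14 | p<.05 only | 20.4/23.0 | 2.2/8.3 |
| +4/+8/+11 | p<.05 or standardised difference >0.2 | 20.0/15.7 | 7.4/10.0 |
| +4/+8/+11 | p<.05 only | 23.9/21.7 | 10.0/13.5 |

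With no effect, any-verdict disagreement was 4.3/6.5% and 5.2/7.8% on the two readings. Under the SAP rule severity was kept in 95/94% of null trials but in only 53/51% at the protocol's 11 to 14 point range. Forcing severity alone into the SAP model changed some verdict in 5.7/11.7% at that range. Month versus window alone changed some verdict in 5.2/7.0% there and 11.7/4.8% at the stepped effects.

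**The case against.** **The SAP governs.** It is titled for the primary paper, states an algorithm, and was written with the protocol in view, since it marks items as in or not in the protocol. An analyst of the primary paper would naturally use it. This is largely right. What remains is that neither document says so, the SAP flags other departures but not this one, and following the SAP still leaves the time unit undecided.

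**The dates.** A reader might infer that the protocol rule was reaffirmed or takes precedence, because that version is dated January 6, 2023 and the SAP 19 May 2022. The documents do not support this. The 2023 version reports that the study has ended while still carrying future-tense planning text, so survival of the earlier rule shows nothing about intent.

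**The randomisation factors.** A reader might count their absence from the forced terms as another conflict. It is not one: neither text forces them. Adding them is an improvement.

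**The simulated rates.** The ICCs, severity gradient, covariate effects and numerical meaning of a substantial clinical difference are not in the documents. The last choice alone moves one figure from 10.0% to 20.4%. A cut-off of 0.2 hardly screens practice-level covariates: in an unstratified check with 11 practices per arm, chance alone exceeded it about 96% of the time. Counting any of four verdicts picks up near-threshold flips, and the time-unit result shows that part of this is ordinary model sensitivity. The simulation also used 3,324 patients, while the protocol expects more. All of this stands, so the rates are not used to size the problem.

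**Limited harm.** The SAP also reports a so-called unadjusted model, free of screening, with cancer type and time fixed. True, but the primary test is not placed on it.

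**Conclusion.** The inconsistency holds and can be read from the text alone. It concerns the model that carries the primary test, on three counts: the entry and retention rule, whether severity is guaranteed, and the unit of the time term. Its certain size is structural: severity always included versus droppable, and up to 47 versus 15 time-by-site parameters over two years. The simulations establish only that the rules can lead to different models and verdicts; how often in this trial is unknown. A reader might infer that the screening inflates type I error, that the SAP excludes severity, or that a fixed list would gain power. None of these is shown: the null rejection rates did not separate the rules, severity is a candidate rather than excluded, and no power comparison is claimed. The point should be fixed because the primary result needs one definition; it does not invalidate the trial.

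**What to change.** State which text governs and align the other with it. The shortest repair is to declare the SAP governing, settle severity's status and name one time unit. That removes the contradiction but leaves the primary model dependent on the estimated arm effects.

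The better repair is one fixed list, identical in both documents:
- cancer type;
- severity of abnormality, as the protocol already says;
- practice size, percent female and percent Medicaid, the randomisation factors;
- one time unit by site, for example the 3-month window, which spares parameters.

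Keep change-in-estimate selection only as a labelled sensitivity analysis. Use the same list for the 240-day and time-to-follow-up models.

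The protocol says the study has ended. If arm-level outcomes have already been seen, a new list is itself post hoc. In that case disclose which rule was used and report the fixed-list model beside that result, not in its place.

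**Cost.** Severity has three levels, so 2 patient-level degrees of freedom, and the screening abnormality is already a listed data element. With at most 44 practices, four arm means, a site effect and three linear randomisation factors, at most 44 − 4 − 4 = 36 between-practice degrees of freedom remain; categorical strata would leave fewer. Otherwise the cost is wording and one extra reported model.
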